# **Amendment History:**

Date	Amendment Number	Region	
08 June 2017	Initial version	Global	
15 August 2017	01	Global	
19 March 2018	02	Global	

#### 1.0 STUDY SUMMARY

Name of Sponsor:	Compound:
Takeda Development Center Americas, Inc. [name]	TAK-831
Study Identifier: TAK-831-1005	Phase: 1

**Protocol Title:** A Randomized, Investigator and Subject Blinded, Sponsor Unblinded, Placebo-Controlled, Phase 1 Study to Evaluate Safety, Tolerability, and Pharmacokinetics of Escalating Multiple Doses of TAK-831 in Healthy Subjects

#### Trial Design:

The study is an investigator and subject blinded, sponsor unblinded, placebo-controlled clinical study progressively assessing independent cohorts of healthy subjects to continue evaluation of the safety, tolerability, and pharmacokinetics (PK) of escalating multiple doses of TAK-831 at doses higher than those achieved in the initial multiple rising dose study (TAK-831-1001).

Up to 6 cohorts will be run either singly or in parallel as non- cerebrospinal fluid (CSF) cohorts with plasma analysis or CSF cohorts with CSF analysis in addition to plasma analysis to assess TAK-831 exposure and levels in the central nervous system (CNS). After meeting all the selection criteria, there will be 8 subjects enrolled in each cohort. They will be randomized on Day 1 in a 1:3 ratio to receive placebo or TAK-831.

In CSF cohorts, lumbar CSF samples will be collected through either a single lumbar puncture or an indwelling temporary catheter on 2 separate occasions. In CSF cohorts that use an indwelling temporary catheter on both occasions, the first collection will occur on Day 1 and the second on Day 16. In CSF cohorts where the predose CSF sample is collected through a single lumbar puncture, the first CSF sample will be collected on Day -1 prior to the start of collection will be obtained through use of an indwelling temporary catheter on Day 16. If an indwelling temporary catheter is being used, it will collect serial CSF samples for 24 hours.

CCL

Subjects in each cohort will be confined during dosing and be kept in the study unit for 24 hours after the last dose for non-CSF cohorts and 48 hours after catheter removal in CSF cohorts. The total confinement period in non-CSF cohorts will be 19 days (Day -2 to Day 17), 20 days in CSF cohorts where an indwelling temporary catheter is being used on Day 1 and Day 16 (confinement from Day -1 to Day 19); and 21 days in CSF cohorts where CSF is collected through a single predose lumbar puncture on Day -1 and through an indwelling catheter on Day 16 (confinement from Day -2 to Day 19). Follow-up assessments will occur on Day 30 (±2) for all cohorts. An exception to these minimum confinement periods will be made if a determination is made to evaluate QT/QTc intervals for additional single doses of TAK-831 in non-CSF cohorts based on the established tolerated dose range.

#### **Trial Primary Objective:**

To evaluate the safety and tolerability of TAK-831 when administered as multiple oral doses at escalating dose levels in healthy subjects.

#### **Secondary Objectives:**

To evaluate the PK of TAK-831 when administered as multiple oral doses at escalating dose levels in healthy subjects.

**Trial Subject Population:** Healthy male subjects and female subjects not of childbearing potential, aged 18 to 55 years, inclusive.

Planned Number of Subjects:	Planned Number of Sites:
Approximately 48 (8 per cohort, up to 6 cohorts)	1

Dose Levels:	Route of Administration:
Starting dose TAK-831 600 mg (tablet T2 formulation, Cohort 1) and 800 mg (suspension formulation, Cohort 2) and matching placebo	Oral
Duration of Treatment:	Planned Trial Duration:
One day for SD part (followed by evaluation for 2 days) and then 14 days for MD part.	Approximately 58 days for each cohort: screening 28 days, treatment and assessments including follow-up 30 days (treatment Days 1 and 3 to 16; assessments Days 1 to 17 for non-CSF cohorts or 1 to 19 for CSF cohorts; follow-up: Day 30 [±2]). Maximum duration: approximately 348 days for 6 cohorts.

#### Main Criteria for Inclusion for Healthy Subjects:

In order to be eligible for participation, subjects must:

- Be a healthy adult male or female not of childbearing potential.
- Be aged 18 to 55 years, inclusive, at the time of informed consent and first study drug dose.
- Weigh at least 45 kg and has a body mass index between 18.0 and 30.0 kg/m^2, inclusive at Screening.

#### Main Criteria for Exclusion for Healthy Subjects:

The subject must be excluded from participating in the study if the subject:

- Has a known hypersensitivity to any component of the formulation of TAK-831.
- Has a risk of suicide according to the investigator's clinical judgment (eg, per Columbia–Suicide Severity Rating Scale), or has made a suicide attempt in the previous 6 months.

#### Additional Exclusion Criteria for Cohort(s) with CSF Collection:

The subject must be excluded from participating in the study if the subject:

- Has had CSF collection performed within 30 days before Check-in (Day -1).
- Has a known hypersensitivity to the anesthetic or its derivatives used during CSF collection, or any medication used to prepare the area of lumbar puncture.
- Has significant vertebral deformities (scoliosis or kyphosis) which, in the opinion of the investigator, may interfere with lumbar puncture procedure.
- Has a history of clinically significant back pain and/or injury.
- Has local infection at the puncture site.
- Has thrombocytopenia or other suspected bleeding tendencies noted before procedure.
- Has developed signs and symptoms of spinal radiculopathy, including lower extremity pain and paresthesia.
- Has any focal neurological deficit that might suggest an increase in intracranial pressure.
- Has any abnormal finding on ophthalmological assessment/fundoscopy suggestive of raised intracranial pressure (ie, optic disc swelling/edema; (uncontrolled) hypertensive retinopathy).
- Suffers regularly from moderate to severe headaches requiring analgesics.
- Subjects with lower spinal malformations (on physical examination or lumbar spine radiography), local spinal infection, or other abnormalities that would exclude lumbar puncture (LP).

#### Main Criteria for Evaluation and Analyses:

#### **Primary Endpoints**

Primary endpoints are the safety parameters of TAK-831 and will be assessed as follows:

1. Percentage of subjects who experience at least 1 treatment-emergent adverse event (TEAE).

- 2. Percentage of subjects who meet the markedly abnormal criteria for safety laboratory tests at least once postdose.
- 3. Percentage of subjects who meet the markedly abnormal criteria for vital sign measurements at least once postdose.
- 4. Percentage of subjects who meet the markedly abnormal criteria for safety electrocardiogram (ECG) parameters at least once postdose.

#### **Secondary Endpoints**

Secondary endpoints are the plasma PK parameters of TAK-831 and will be measured as follows:

- 1. Maximum observed plasma concentration  $(C_{max})$  (Day 1).
- 2. Maximum observed steady-state plasma concentration during a dosing interval (Day 16).
- 3. Time of first occurrence of  $C_{max}$  (Days 1 and 16).
- 4. Area under the plasma concentration-time curve during a dosing interval (Days 1 and 16).

#### **Statistical Considerations:**

#### Safety:

Adverse events will be presented in listings, and TEAEs will be summarized. Individual results of laboratory tests (hematology, chemistry, and urinalysis) will be listed and Baseline, postdose, and changes from Baseline to postdose laboratory data will be summarized. Individual results of vital signs will be listed and Baseline, postdose, and changes from Baseline in vital signs will be summarized. Individual results of quantitative ECG parameters from the 12-lead safety ECGs will be listed and Baseline, postdose, and changes from Baseline in quantitative ECG parameters will be summarized. All summaries will be performed by regimen for placebo, each TAK-831 dose level, and TAK-831 overall. Other safety measures (neurological examination and the ophthalmoscopic assessment of the fundus, physical examination findings and suicidality assessments [C-SSRS]) will be presented in data listings.

#### PK Measures:

Concentrations of TAK-831 in plasma (all cohorts) and CSF (CSF Cohort[s]) will be summarized by dose, drug formulation, and day over each scheduled sampling time using descriptive statistics. Individual plasma concentration data versus time will be presented in a data listing. Plasma and CSF PK parameters, including dose-normalized  $C_{max}$  and AUCs, will be summarized by dose, drug formulation, and day using descriptive statistics. Changes in the PK parameters from Day 1 to Day 16 will be assessed by summarizing the ratio of Day 16 to Day 1 by dose. Dose proportionality in plasma PK parameters ( $C_{max}$  and AUCs) will be assessed graphically for Day 1 and Day 16 plasma concentrations. Additional analyses will be included as appropriate.

Biomarker Measures and Exploratory Endpoints:

#### **Sample Size Justification:**

The sample size chosen of 8 subjects for all cohorts (6 active:2 placebo) is considered to be sufficient for the determination of progression to the next cohort based on the safety and PK data. The sample size was not based on statistical power considerations.

# 1.1 Protocol Amendment No. 02 Summary of Changes

#### Rationale for Amendment No. 02

This document describes the changes in reference to the protocol incorporating Amendment No. 02. The primary reason for this amendment is to revise the study procedures to enable cohorts that obtain measurements as described in the previous protocol in addition to the collection of a baseline CSF sample on Day -1 through a single lumbar puncture and serial CSF sampling on Day 16. In addition, the drug supply management has been updated. Clarifications, inconsistencies, and minor grammatical, editorial, and formatting changes are included for clarification purposes only.

For specific description of text changes and where the changes are located, see Appendix E.

# Changes in Amendment No. 02

- 1. Updated study design and procedures.
- 2. Updated clinical study material management.

# 2.0 STUDY SCHEMATIC

Cohorts	Pretreatme	nt Period	nents (a)				
(up to 6 as		Check-in/	SD	Part			Follow-
needed)	Screening	Baseline	Treatment	Evaluation	MD Part	Study Exit	up (b)
Non-CSF (or	Days -28 to -3	Day -2	Day 1	Days 1 to 2	Days 3 to	Day 17 (non-CSF	Day 30
CSF cohorts					16	cohort) / Day 19	(±2)
that collect						(CSF cohort	
Day -1 CSF						where Day -1	
samples via a						CSF is collected	
single predose						via a single	
lumbar						predose lumbar	
puncture)						puncture)	
CSF	Days -28 to -2	Day -1	Day 1	Days 1 to 2	Days 3 to	Day 19	Day 30
		-		-	16	-	(±2)
		+		Confinem	ent	→	

CSF=cerebrospinal fluid, MD=multiple dose, PD=pharmacodynamic, PK=pharmacodynamic, SD=single dose.

a) TAK-831 dosing will be on Day 1 for SD and Days 3 through 16 for MD.

b) The Follow-up Visit will occur by telephone unless abnormal, clinically significant findings are observed upon discharge. In these cases, subjects may then be brought back to the clinic for re-evaluation per investigator's discretion.

# 3.0 SCHEDULE OF STUDY PROCEDURES

	Scr- een-i ng	Check in / Baseline Assessments						Т	reat	men	t Da	ny							Study Exit (a)		Follow- up
Study Day:	-28 to -3	Day -2 (non-CSF or CSF cohorts) that collect baseline CSF samples via a single predose lumbar puncture or Day -1 (CSF cohorts)	1	2	3	4	5	6	7	8	9	10	11	12	13	14	15	16	Day 17 (non-C SF) / Day 19 (CSF)	Early Termina- tion (b)	30 (±2) (c)
 		VE PROCEDURES																			_
Informed consent Inclusion/exclusion	X	X	X																		
criteria  Demographics/ medical history	X																				
Medication history	X	X																			
Concurrent medical conditions	X	X																			
CLINICAL	PRO	CEDURES/ASSESSMI	ENTS																		
Full physical examination	X	X																	X	X	(X)
Height	X																				
Weight and BMI (d)	X																		X	X	(X)
Concomitant medications (e)	X	X	X	X	X	X	X	X	X	X	X	X	X	X	X	X			X	X	X
Vital signs (f)	X	X	X	X	X	X	X	X	X	X	X	X	X	X	X	X		X	X	X	(X)
Neurological examination and fundoscopy (g)		X															X				
Lumbar spine radiography (for CSF cohorts only) (h)	X																				

	Scr- een-i ng	Check in / Baseline Assessments		ı				Т	reat	men	t Da	ıy							Study Exit (a)		Follow- up
Study Day:	-28 to -3	Day -2 (non-CSF or CSF cohorts) that collect baseline CSF samples via a single predose lumbar puncture or Day -1 (CSF cohorts)	1	2	3	4	5	6	7	8	9	10	11	12	13	14	15	16	Day 17 (non-C SF) / Day 19 (CSF)	Early Termina- tion (b)	30 (±2) (c)
Safety ECG (i)	X	X	X									X						X	X	X	(X)
CCI																					
C-SSRS (k)	X	X																	X	X	
Study drug administration			X		X	X	X	X	X	X	X	X	X	X	X	X	X	X			
AE assessment		X	X	X	X	X	X	X	X	X	X	X	X	X	X	X	X	X	X	X	X
		PROCEDURES																			
Clinical laboratory tests (1)	X	X	X									X							X	X	(X)
Hepatitis panel (HBsAg and anti-HCV)	X																				
HIV screen	X																				
FSH (m)	X																				
hCG (n)	X	X																	X	X	(X)
Hormone laboratory tests (o)			X																X	X	(X)
Drug screen	X	X																			
PGx EVAL	UATI	ONS																			
DNA sample collection			X																		
(p) PK EVALU		INC																			
PK blood collection (q)	ATIU	NO	X	X								X			X			X		X	
PK CSF collection (r)		X (r)	1	X (r)								71			1			X		Λ	

	Scr- een-i ng	Check in / Baseline Assessments						Т	reat	men	t Da	ıy							Study Exit (a)		Follow- up
		Day -2 (non-CSF or																			
		CSF cohorts) that																			
		collect baseline CSF																	Day 17		
		samples via a single																	(non-C	Early	
		predose lumbar																	SF)/	Termina-	
	-28	puncture or Day -1																	Day 19	tion	30
Study Day:	to -3	(CSF cohorts)	1	2	3	4	5	6	7	8	9	10	11	12	13	14	15	16		(b)	(±2) (c)

#### PD/BIOMARKER EVALUATIONS

CCI

CCI

AE=adverse event, anti-HCV=antibody to hepatitis C virus, BMI=body mass index, C-SSRS=Columbia–Suicide Severity Rating Scale, ECG=electrocardiogram, FSH=follicle-stimulating hormone, HbA1c=glycosylated hemoglobin, HBsAg=hepatitis B surface antigen, hCG=human chorionic gonadotropin, HIV=human immunodeficiency syndrome, PGx=pharmacogenomics, TSH=thyrotropin.

- (a) Study exit for non-CSF cohorts occurs on Day 17 and for CSF cohorts on Day 19.
- (b) At Early Termination, perform all procedures per Section 7.6.
- (c) The Follow-up Visit will occur by telephone on Day 30 (±2) unless abnormal, clinically significant findings are observed upon discharge. In these cases, subjects must be brought back to the clinic for re-evaluation per investigator's discretion. (X) is for optional procedure.
- (d) BMI will be calculated only at Screening.
- (e) Record all ongoing medications from Screening and throughout the study.
- (f) Vital signs (oral temperature, respiratory rate, pulse, and blood pressure) will be obtained at Screening, Check-in, Day 1, and Days 3 through 16 at predose (within 60 minutes before dosing) and at 1, 4, and 12 hours after the morning dose, and Study Exit/Early Termination and as appropriate at the Follow-up Visit. Day 2 vital signs should be collected approximately 24 hours after the Day 1 dose is administered. Pulse and blood pressure will be measured after 5 minutes supine and again at 1 and 3 minutes after standing for all scheduled time points, with exception of Day 1, Day 2, and Day 16 in cohorts where CSF collection is performed using an indwelling catheter, when only supine measurements will be taken.
- (g) Only for CSF cohorts: A neurological assessment and eye examination (ophthalmological assessment of the retina, fundoscopy) will be performed on Day -2 (baseline collection through single lumbar puncture), Day -1 (baseline collection through indwelling catheter) and Day 15.
- (h) Lumbar spine radiography (for CSF cohorts only) if one has not been performed within the past 12 months prior to the screening visit.
- (i) A standard 12-lead ECG (single) will be recorded at Screening, Check-in, Day 1 (predose [within 60 minutes prior to dosing], and at 1.5 hour postdose (morning dose), Day 16 (predose [within 60 minutes prior to dosing], and at 1 and 2 hours after morning dose, Day 10 (predose), and Study Exit/Early Termination and as appropriate at the Follow-up Visit.

**Protocol Incorporating Amendment No. 02** 

- (k) The C-SSRS (Lifetime/Recent) will be administered at Screening; the C-SSRS (since last visit) will be administered at Check-in and at Study Exit/Early Termination.
- (l) Clinical laboratory tests (hematology, serum chemistry, and urinalysis) will be collected at Screening, Check-in, and after a 10-hour fast at predose on Days 1, 10, and at Study Exit/Early Termination and as appropriate at the Follow-up Visit.
- (m) For women only: A FSH level will be obtained on postmenopausal women at Screening only.
- (n) For women only: Serum hCG will be performed at Screening, Day -1, and Study Exit/Early Termination, and at the Follow-up Visit if the subject is brought back to the clinic for re-evaluation.
- (o) Hormone laboratory tests (prolactin, growth hormone, cortisol, and TSH) will be collected on Day 1 (before dosing, under fasted conditions and 3 hours postdose) and at Study Exit/Early Termination (morning values, under fasted conditions) and as appropriate at the Follow-up Visit.
- (p) One blood sample (6 mL) will be collected for DNA analysis before dosing on Day 1.
- (q) Blood samples (4 mL) for PK analyses will be collected on Day 1 (within 30 minutes before dosing) and at 0.5, 1, 1.5, 2, 4, 8, 12, 24, hours after the morning dose; on Day 10 (predose), Day 13 (predose), and on Day 16 at predose (within 30 minutes before dosing), and at 0.5, 1, 2, 4, 8, 12, 16, and 24 hours after the morning dose and at Early Termination.

CCI

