# 11.1.3 PK Analysis

Concentrations of TAK-831 in plasma (all cohorts) and CSF (CSF Cohort[s]) will be summarized by dose, drug formulation, and day over each scheduled sampling time using descriptive statistics. Individual plasma concentration data versus time will be presented in a data listing.

PK parameters of TAK-831 will be derived using noncompartmental analysis methods. The PK parameters of TAK-831 will be determined from the concentration-time data for all evaluable subjects. Actual sampling times, rather than scheduled sampling times, will be used in all computations involving sampling times. Plasma and CSF PK parameters, including dose-normalized Cmax and AUCs, will be summarized by dose, drug formulation, and day using descriptive statistics. Changes in the PK parameters from Day 1 to Day 16 will be assessed by summarizing the ratio of Day 16 to Day 1 by dose and drug formulation. Dose proportionality in plasma PK parameters (Cmax and AUCs) will be assessed graphically for Day 1 and Day 16 plasma concentrations for each formulation. Additional analyses will be included if appropriate.

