8.9 Pharmacokinetic/Pharmacodynamic Analysis

8.9.1 Pharmacokinetic Analysis

All PK summaries and analyses will be based on the PK set. PK parameters of TAK-831 will be derived using non-compartmental analysis methods. The PK parameters of TAK-831 will be determined from the concentration-time data for all evaluable subjects. Actual sampling times, rather than scheduled sampling times, will be used in all computations involving sampling times.

Serial blood samples for determination of TAK-831 concentrations will be collected on Day 1 (within 30 minutes before dosing) and at 0.5, 1, 1.5, 2, 4, 8, 12, 24, hours after the morning dose; on Day 10 (predose), Day 13 (predose), and on Day 16 at predose (within 30 minutes before dosing), and at 0.5, 1, 2, 4, 8, 12, 16, and 24 hours after the morning dose and at Early Termination.

In CSF cohorts, serial CSF samples will be collected On Day 1 and/or Day 16 at predose (within 30 minutes before dosing) and at 1, 4, 8, 12, and 24 hours after the morning dose.

The following pharmacokinetic parameters will be calculated for plasma (Day -1, Day 1 and Day 16) and CSF (Days 1 and/or 16) concentrations of TAK-831 when appropriate:

Symbol/Term	Definition
$AUC_{\tau} / AUC_{\tau, CSF}$	Area under the concentration-time curve during a dosing interval.
$AUC_t / AUC_{t, CSF}$	Area under the concentration-time curve from time 0 to time t. (Day 1 only)
AUC_{∞}	Area under the concentration-time curve from time 0 to infinity, calculated using the observed value of the last quantifiable concentration (Day 1 only)
$R_{ac(AUC)} / R_{ac(AUC, CSF)}$	Accumulation ratio based on AUC_{τ} .
$R_{ac(C_{max})} / R_{ac(C_{max}, CSF)}$	Accumulation factor based on C_{max} .
$C_{av,ss} / C_{av,ss, CSF}$	Average concentration during a dosing interval, at steady state.
$C_{max} / C_{max, CSF}$	Maximum observed concentration on Day 1 and Day 16.
CL/F	Apparent clearance after extravascular administration, calculated as $=Dose/AUC_{\infty}$ after a single dose. Plasma only. (Day 1 only)
λ_z	Terminal disposition phase rate constant. Plasma only.
$t_{1/2z}$	Terminal disposition phase half-life. Plasma only.
$t_{max} / t_{max, CSF}$	Time of first occurrence of C_{max} .
V_z / F	Apparent volume of distribution during the terminal disposition phase after extravascular administration, calculated using the observed value of the last quantifiable concentration. Plasma only. (Day 1 only)

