Descriptive statistics (N, arithmetic mean, SD, %CV, median, minimum, and maximum) will be used to summarize the plasma and CSF PK parameters for TAK-831, including dose-normalized C_{max} and AUCs, by dose and formulation. In addition, geometric mean will be computed for C_{max} and AUCs, including those dose-normalized C_{max} and AUCs. Individual plasma PK parameters will be presented in a data listing.

Dose proportionality in plasma and CSF PK parameters (C_{max} and AUCs as well as dose-normalized C_{max} and AUCs) will be assessed graphically using box-plots for Day 1 and Day 16 plasma and CSF PK parameters for each formulation. Other figures needed for PK data are described in Clinical pharmacology Analysis Plan for this study.

Additional analyses will be included if appropriate.

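### Day 16/Day 1 PK ratios are formed on unequal plasma sampling grids (1.5 h on Day 1 only, 16 h on Day 16 only), so Rac(Cmax) can read a few percent low if peaks fall at about 1.2-1.8 h; a common-time ratio would remove this

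*Protocol*

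**What the plan says.** Protocol 3.0, footnote (q), sets the plasma times. Day 1 is sampled before dosing "and at 0.5, 1, 1.5, 2, 4, 8, 12, 24, hours after the morning dose". Day 16 is sampled at predose "and at 0.5, 1, 2, 4, 8, 12, 16, and 24 hours after the morning dose". SAP 8.9.1 gives the same two lists.

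Protocol 11.1.3 describes how the two days will be compared. Between-day change "will be assessed by summarizing the ratio of Day 16 to Day 1 by dose and drug formulation". The parameter table in SAP 8.9.1 adds accumulation ratios based on Cmax and on AUCtau. The planned statistics are broad: "Descriptive statistics (N, arithmetic mean, SD, %CV, median, minimum, and maximum) will be used to summarize the plasma and CSF PK parameters".

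Three provisions touch on the point without settling it:
- SAP 8.9.1 uses actual rather than scheduled sampling times.
- It leaves room for more work: "Additional analyses will be included if appropriate".
- It cites a Clinical Pharmacology Analysis Plan for other PK figures. That plan is not among the supplied documents.

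Protocol 6.4 also lets the sampling scheme be modified during the trial.

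**The concern.** Observed Cmax is the largest of the measured concentrations. A day with an extra sample near the peak tends to give a larger Cmax, even when the true profile is unchanged. Here the extra sample (1.5 h) is on Day 1, the denominator of the ratio. If peaks fall between the 1 h and 2 h samples, Rac(Cmax) is pulled down in every cohort in the same direction, so pooling cohorts does not average it out. Actual sampling times do not help, because the sample is absent rather than mistimed.

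The 16 h sample has no bearing on Cmax. It enters only the AUC ratio, where it splits the 12-24 h interval on Day 16 but not on Day 1.

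Day 1 Cmax, Day 16 steady-state Cmax, and AUC on both days are secondary endpoints, and the ratio is the planned summary of change between the days. A shift produced by the grids could be read as a change in the drug's kinetics.

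**Working it through.** The plan states no accumulation figure, so there is nothing to reproduce.

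**Grids.** Day 1 only: 1.5 h. Day 16 only: 16 h. Common: predose, 0.5, 1, 2, 4, 8, 12 and 24 h.

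**Inputs from the documents (protocol 6.3.2 and Table 6.b).** AUC24/Cmax describes how narrow the peak is:
- 400 mg suspension: 3454/1270 = 2.72 h.
- 600 mg T2 tablet, projected: (0.83 x 3454)/(0.60 x 1270) = 2866.8/762 = 3.76 h.

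**Assumed.** The time of peak, the curve shape and the noise. The documents give none of these.

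**Step 1: no noise, same true profile on both days.** Take C(t) = (t/tm)^a exp{a(1 - t/tm)}, with its peak at tm. Choose a so that AUC/Cmax = tm e^a Γ(a+1)/a^(a+1) equals 2.72 or 3.76 h. The bias is max C on the Day 16 grid / max C on the Day 1 grid - 1.

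The 1.5 h sample matters only if it exceeds both neighbours:
- above the 1 h value: tm > 0.5/ln(1.5) = 1.23 h;
- above the 2 h value: tm < 0.5/ln(2/1.5) = 1.74 h.

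The worst case is where the 1 h and 2 h values are equal, at tm = 1/ln 2 = 1.44 h:
- suspension width (a = 1.93): 0.891/0.9985 - 1 = -10.7%;
- tablet width (a = 1.08): 0.938/0.9992 - 1 = -6.1%.

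At tm = 1.5 h the figures are -9.0% and -5.1%. At 1.2, 1.8 and 2.0 h they are 0.

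**Step 2: 10% lognormal noise on each sample, same profiles** (200,000 simulated subjects per case). Bias in the geometric mean ratio:

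| True peak (h) | Suspension width | Tablet width |
|---|---|---|
| 0.8 | -0.4% | -1.0% |
| 1.0 | -1.8% | -2.2% |
| 1.2 | -4.4% | -3.9% |
| 1.5 | -8.4% | -5.6% |
| 1.8 | -4.2% | -4.5% |
| 2.0 | -1.3% | -2.6% |

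Noise widens the window because the Day 1 maximum is taken over one more near-peak sample. The median, which is a planned statistic, moves as much (-8.4% and -5.5% at 1.5 h). If the peak time also varies between occasions, the bias across 1.2-2.0 h is -3.3% to -5.8% at 20% variability and -2.7% to -3.8% at 40%. On common times it is within 0.1% of zero.

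**Step 3: flatter curves with real accumulation, no noise** (one compartment, single dose against 24 h steady state, peak at 1.45 h). The bias is -4.8%, -3.4%, -2.2% and -0.35% for half-lives of 2, 4, 8 and 24 h. At 4 h, a true ratio of 1.018 reads 0.983. On common times, all one-compartment cases with half-lives of 1-24 h are within 0.7% of the true ratio.

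**Step 4: AUC ratio, same one-compartment cases.** The linear trapezoid gives about 0 to -3.4%, mostly from the 16 h sample. Linear-up/log-down gives -0.9% to +0.2%. On common times the linear trapezoid is off by at most +0.25%. The supplied documents do not say which rule will be used.

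**The case against.** The case for leaving the plan alone is strong on consequence.

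- **No tmax or absorption lag is documented.** If peaks come at 0.8 h or earlier, the effect is 1% or less and the remedy changes almost nothing. The only half-life clue is the contraception window, where 95 - 90 = 5 days stands for five half-lives, about 24 h if read literally. If decline around the peak were that slow, the noise-free bias would be below 1%. This stands, and it is why the size is conditional. The AUC24/Cmax figures of 2.72 and 3.76 h do, however, point to a fairly narrow peak.
- **The window is narrow.** A reader might infer that any peak between 1 and 2 h gives a large bias. Without noise the range is only 1.23-1.74 h, and with noise the effect fades towards 2 h.
- **Not every summary need read low.** The arithmetic mean of individual ratios is itself skewed upward. For independent occasions with equal CV and a true ratio of 1, its expectation is 1 + CV², which is +4% at 20% and +9% at 30%. That can offset or reverse the grid effect in the mean, but not in the median.
- **No decision depends on it.** A reader might infer that escalation is exposed. The criteria in protocol 6.2 use mean Cmax and AUC24 limits, a plateau across the two highest dose cohorts, and safety events. None uses the ratio.
- **Precision is low.** With 6 active subjects, a 90% interval for the ratio spans a factor of 1.26 to 1.57 either way at assumed per-occasion CVs of 20-40%. A shift of a few percent is small beside that.
- **The analysis may be planned elsewhere.** The Clinical Pharmacology Analysis Plan was not supplied. It is cited only for figures, but the supportable statement is that the supplied protocol and SAP contain no common-time ratio.
- **It can be done later.** Individual concentrations are listed, so nothing is lost. That is true, but a comparison specified in advance is easier to defend than one added after an odd ratio is seen.

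**Conclusion.** The point holds as a low-stakes improvement. The grids differ, the planned ratios use them as they stand, and the supplied documents name no like-for-like version. For Rac(Cmax) the effect is downward and conditional on an undocumented peak time. Without noise it reaches about 6% (tablet width) to 11% (suspension width) near 1.44 h and is nil outside 1.23-1.74 h. With an assumed 10% noise it is about -3% to -8% for peaks at 1.2-1.8 h, about -2% at 1.0 h, and 1% or less at 0.8 h or earlier. The effect on Rac(AUC) is about 0 to -3% with a linear trapezoid and less with log-down.

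The documents do not support the stronger reading that accumulation will be understated by a known amount. Nor do they show that the secondary endpoints themselves are invalid: Cmax and AUC on each day remain properly defined on that day's grid. The artefact lies in comparing the two days.

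**What to change.** In SAP 8.9.1, add that the Day 16/Day 1 ratios of plasma Cmax and AUCtau will also be computed from the times common to both days (predose, 0.5, 1, 2, 4, 8, 12 and 24 h) and shown beside the full-grid ratios. Keep the full grids for the stand-alone Day 1 and Day 16 parameters. The SAP's allowance for additional analyses already covers this.

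The cost is one or two sentences of SAP text and a few table rows. The common-time ratios are slightly coarser, because they set aside the 1.5 h and 16 h samples. No new samples are needed. Adding a 1.5 h sample on Day 16 in later cohorts only would be a worse remedy: Day 16 grids would then differ between cohorts within the planned dose-proportionality box-plots.
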